1.3. Summary of Benefit/Risk Assessment

An evaluation of the anticipated benefits and risks as required in Article 3(2)(a) of Directive 2001/20/EC (cf. Article 6(3)(b) of Directive 2001/20/EC) has been conducted.

Available adverse event and laboratory abnormality data from patients with advanced solid tumors treated with single-agent avelumab suggest an acceptable safety profile of the compound. Most of the observed events were either in line with those expected in patients with advanced solid tumors or with similar class effects of monoclonal antibodies blocking the PD-1/PD-L1 axis. Infusion-related reactions including hypersensitivity and immune related Adverse Events (irAEs)/autoimmune disorders have been identified as important risks for avelumab. Respective risk mitigation measures have been implemented in all ongoing clinical studies with avelumab, including this clinical trial protocol. These include a treatment algorithm and guidelines for treatment interruption and discontinuation in case of irAEs, as well as mandatory pre-treatment with a histamine H1 receptor (H1) blocker and acetaminophen. Avelumab demonstrated clinical activity in heavily pretreated ovarian cancer patients in an expansion cohort of an ongoing Phase 1 study.

Chemotherapy including doxorubicin has recently been shown to have immunostimulatory properties.⁵² In preclinical studies, combination of avelumab with chemotherapies showed improved anti-tumor activity of chemotherapy (gemcitabine, oxaliplatin, 5FU).¹

PLD is approved multinationally for the treatment of patients with ovarian cancer whose disease has progressed or recurred after platinum-based chemotherapy. PLD is generally well-tolerated with a well-characterized toxicity profile. Currently there are no published reports of doxorubicin combined with immune checkpoint inhibitors. The literature suggests a low possibility of overlapping toxicities for avelumab and PLD. Close safety monitoring will be performed throughout the study as outlined in [Section 3.1](#).

Thus, the projected benefit/risk of avelumab given in combination with PLD is anticipated to be favorable for investigation in this advanced cancer patient population.

2. STUDY OBJECTIVES AND ENDPOINTS

2.1. Objectives

Primary Objectives

- To demonstrate that avelumab given alone or in combination with PLD is superior to PLD alone in prolonging OS in patients with platinum -resistant/platinum-refractory ovarian cancer.
- To demonstrate that avelumab given alone or in combination with PLD is superior to PLD alone in prolonging Progression Free Survival (PFS) in patients with platinum-resistant/platinum-refractory ovarian cancer.

Secondary Objectives

- To evaluate anti-tumor activity of avelumab given alone or in combination with PLD versus PLD alone in ovarian cancer patients.
- To evaluate the overall safety profile of avelumab alone or in combination with PLD versus PLD alone in ovarian cancer patients.
- To characterize the PK of doxorubicin (PLD samples) and avelumab when administered in combination, and to assess the effect of avelumab on the PK of doxorubicin (PLD sample) and the effect of PLD on PK of avelumab.
- To assess the immunogenicity of avelumab.
- To evaluate candidate predictive biomarkers of sensitivity or resistance to avelumab or PLD in combination with avelumab in pre-treatment tumor tissue, that may aid in the identification of patient subpopulations most likely to benefit from treatment.
- To compare the effect of avelumab alone or in combination with PLD versus PLD alone on patient-reported outcomes (PRO) in patients with ovarian cancer.

Exploratory Objectives

- [REDACTED]
- [REDACTED]

2.2. Endpoints

Primary Endpoints

- Overall survival (OS).
- Progression Free Survival as determined by Blinded Independent Central Review according to RECIST version 1.1.

Secondary Endpoints

- Efficacy: Objective response (OR), Duration of Response (DR), and Disease Control (DC) as determined by Blinded Independent Central Review (BICR) and Investigator [As assessed by RECIST version 1.1]. ([Appendix 3](#)).

- PFS as determined by Investigator according to RECIST version 1.1.
- Safety: AEs (as graded by NCI CTCAE v.4.03); laboratory abnormalities (as graded by NCI CTCAE v.4.03); vital signs (blood pressure, pulse rate); electrocardiograms (ECGs), ECHO or MUGA scans.
- Pharmacokinetics: PK parameters, including C_{trough} and C_{max} for avelumab, C_{max} , volume of distribution (V_d), clearance (CL), area under the concentration-time curve (AUC) for doxorubicin (PLD samples).
- Immunogenicity: Incidence of anti-drug antibodies (ADA) and neutralizing antibodies (Nab) against avelumab.
- Candidate predictive biomarkers in tumor tissue including, but not limited to, PD-L1 expression and tumor infiltrating CD8+ T lymphocytes as assessed by immunohistochemistry (IHC).
- Patient-Reported Outcomes: EORTC QLQ-C30, EORTC QLQ-OV28, and EQ-5D-5L. ([Appendix 6](#)).

Exploratory Endpoints

- **CCI** [REDACTED]
- CA-125 levels.
- **CCI** [REDACTED]

[figure not shown]
3. STUDY DESIGN

3.1. Study Overview

This is a Phase 3, multicenter, randomized, open-label, parallel 3-arm study in which approximately 550 patients will be randomized in a 1:1:1 ratio to receive avelumab alone, avelumab in combination with PLD, or PLD alone, as follows:

- Arm A: avelumab alone;
- Arm B: avelumab plus PLD;
- Arm C: PLD alone.

Figure 1. Study Randomization Design

Patients will be stratified by platinum-refractory or platinum-resistant status, number of prior regimens (1 vs 2 or 3), and bulky disease (defined as presence of a tumor ≥ 5 cm) vs not. Cross-over will not be permitted.

3.1.1. Safety Monitoring

An evaluation of the safety of the avelumab plus PLD arm will be performed during the study as follows:

Randomization to all three arms will begin at the start of the study. When six patients are randomized to the combination arm, enrollment in all arms will be held. After each patient in the combination arm has completed a minimum observation period of 4 weeks, the external data monitoring committee (DMC) will evaluate all available safety data. If there are no safety concerns precluding continuation of the study, enrollment will proceed. Other options may include termination of the combination arm, or enrollment of 6 more patients with an enrollment hold. These decisions will be at discretion of the DMC.

A second safety evaluation will be performed by the external DMC after a total of 20 patients are enrolled on the combination arm and followed for at least 4 weeks, without an enrollment hold. The frequency of subsequent DMC meetings will be determined by the external DMC at the time of the second safety evaluation.

3.1.2. Study Treatment

Avelumab (Arm A, Arm B) 10 mg/kg will be given as a 1-hour intravenous infusion (IV) every 2 weeks (Q2W) in 4-week cycles.

PLD (Arm B, Arm C) 40 mg/m² will be given as a 1-hour IV infusion every 4 weeks (Q4W) in 4-week cycles.

In Arm B, on the days that the patient receives both infusions, PLD should be administered prior to avelumab. See [Section 5.2.3.3](#).

In all patients, study treatment may continue until PD as assessed by the investigator, unacceptable toxicity, patient refusal, patient loss to follow up, or termination of the study by the Sponsor, whichever comes first (see [Section 6.5 Patient Withdrawal](#)). Avelumab and PLD will not be continued beyond initial disease progression. For those patients who are on single-agent avelumab post-progression at the time of amendment approval, if they present with a subsequent scan showing disease progression, they must discontinue avelumab. See [Section 5.2.4](#).

For administration information, see [Section 5.2.3](#). Patients should be monitored closely for toxicity and infusion related reactions. For the management of infusion-related reactions and other toxicities, see [Section 5.2.6](#).

Patients on Arm B who are discontinued from avelumab treatment for any reason, must also be discontinued from PLD (within the scope of this study, if applicable) and entered into the 90 Day Safety Follow-up Period.

Patients on Arm B who discontinue PLD for reasons other than disease progression may continue taking avelumab until withdrawal criteria are met.

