- Patients will be stratified according to platinum-refractory or platinum-resistant status, number of prior regimens (1 vs 2 or 3), and bulky disease (defined as presence of a tumor ≥ 5 cm) vs not.
- The final analysis of this study has been completed; however, this study will remain open to allow the remaining patients currently enrolled in Arm A or Arm B to continue receiving avelumab as a single agent or in combination with PLD. These patients will be allowed to continue receiving avelumab based on the investigator's assessment that the anticipated benefit outweighs the risks.
- The schedule of activities (SOA) found in [Appendix 7](#) is replacing the previous SOA and has been revised to decrease the frequency of study procedures while maintaining appropriate assessment of patient safety.

Study Treatments

Avelumab (Arm A, Arm B) 10 mg/kg will be given as a 1-hour intravenous infusion (IV) every 2 weeks (Q2W) in 4-week cycles.

PLD (Arm B, Arm C) 40 mg/m² will be given as a 1-hour IV infusion every 4 weeks (Q4W) in 4-week cycles.

In all patients, study treatment may continue until PD as assessed by the investigator, unacceptable toxicity, patient refusal, patient loss to follow up, or termination of the study by the Sponsor, whichever comes first (see [Section 6.5](#) Withdrawal). Avelumab and PLD will not be continued beyond disease progression. Patients who are on single-agent avelumab post-progression at the time of amendment approval will be discontinued from avelumab after documentation of a subsequent disease progression. Cross-over will not be permitted. Patients on Arm B who are discontinued from avelumab treatment for any reason, must also be discontinued from PLD (within the scope of this study, if applicable) and entered into the 90 Day Safety Follow-up Period.

Statistical Methods

Sample Size Determination

The primary objectives of this study are to demonstrate that avelumab given alone or in combination with PLD is superior to PLD alone in prolonging OS or PFS in patients with platinum-resistant/refractory ovarian cancer. The study is designed to test in parallel four hypotheses.

- The first null hypothesis is that the true OS hazard rates for PLD alone and avelumab alone arms are the same ($HR=1$) versus the alternative hypothesis that the true hazard rate is smaller in the avelumab alone arm than in the PLD alone arm ($HR<1$).

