5.2.8.1. PLD Single Agent and Avelumab-PLD Combination: Neutropenia and Thrombocytopenia

ANC must be $\geq 1.5 \times 10^9/L$ and the platelet count $\geq 75 \times 10^9/L$ prior to the beginning of the following course of treatment. For patients who do not achieve haematological recovery on scheduled day of PLD treatment, complete blood counts should be performed twice weekly until the above defined limits are achieved. If haematological recovery is achieved within 14 days after the scheduled day of PLD treatment, resume PLD at the previous dose. If haematological recovery is not achieved 14 days or more after the scheduled day of the course, the patient will discontinue treatment. Administration of G-CSF or EPO is permitted according to approved indications and scientific recommendations.

Table 7. PLD Single Agent and Avelumab-PLD Combination: Treatment Modification for Neutropenia and Thrombocytopenia

Neutropenia and Thrombocytopenia	PLD single agent	Avelumab-PLD combination*
Grade 1	No PLD dose reduction/delay	No PLD dose reduction/delay Continue avelumab as per schedule
Grade 2	Delay PLD until toxicity resolves to ANC $\geq 1.5 \times 10^9/L$, platelets $\geq 75 \times 10^9/L$; then resume PLD at previous dose.**	Delay PLD until toxicity resolves to ANC $\geq 1.5 \times 10^9/L$, platelets $\geq 75 \times 10^9/L$; then resume PLD at previous dose.** Continue avelumab as per schedule.

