Grade 3	Delay PLD until toxicity resolves to ANC $\geq 1.5 \times 10^9/L$, platelets $\geq 75 \times 10^9/L$; then resume PLD at previous dose.** If Grade 3 toxicity recurs, follow institutional guidelines.	Delay PLD until toxicity resolves to ANC $\geq 1.5 \times 10^9/L$, platelets $\geq 75 \times 10^9/L$; resume PLD at previous dose.** Continue avelumab as per schedule. If Grade 3 toxicity recurs, delay PLD and avelumab until toxicity resolves to ANC $\geq 1.5 \times 10^9/L$, platelets $\geq 75 \times 10^9/L$; then resume PLD at reduced dose** and avelumab at standard dose. If Grade 3 toxicity recurs with PLD at reduced dose, delay PLD until toxicity resolves to ANC $\geq 1.5 \times 10^9/L$, platelets $\geq 75 \times 10^9/L$; then resume PLD at the next reduced dose. ** For avelumab, 
 • If toxicity resolves to ANC $\geq 1.5 \times 10^9/L$, platelets $\geq 75 \times 10^9/L$ within ≤ 14 days, resume avelumab at the standard dose. • If toxicity resolves to ANC $\geq 1.5 \times 10^9/L$, platelets $\geq 75 \times 10^9/L$ in > 14 days, permanently discontinue avelumab.
Grade 4	Delay PLD until toxicity resolves to ANC $\geq 1.5 \times 10^9/L$, platelets $\geq 75 \times 10^9/L$; then resume PLD at reduced dose level or continue at previous dose with prophylactic granulocyte growth factor support.**	Delay PLD and avelumab until toxicity resolves to Grade ≤ 1 ; then resume PLD at reduced dose level** and avelumab at standard dose. If Grade 4 toxicity recurs with PLD at reduced dose, delay PLD until toxicity resolves to ANC $\geq 1.5 \times 10^9/L$, platelets $\geq 75 \times 10^9/L$; then resume PLD at the next reduced dose. ** For avelumab, 
 • If toxicity resolves to ANC $\geq 1.5 \times 10^9/L$, platelets $\geq 75 \times 10^9/L$ within ≤ 14 days, resume avelumab at the standard dose. • If toxicity resolves to ANC $\geq 1.5 \times 10^9/L$, platelets $\geq 75 \times 10^9/L$ in > 14 days, permanently discontinue avelumab.

* For patients on avelumab alone, refer to [Section 5.2.7.1](#).

**If haematological recovery is achieved within 14 days after the scheduled day of PLD treatment, resume PLD at the previous dose. If PLD is delayed by 1 week, avelumab should be delayed by 1 week so that PLD and avelumab are administered together. If haematological recovery is not achieved 14 days or more after the scheduled day of the course, the patient will permanently discontinue treatment.

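### In Arm B, Table 7 restarts PLD after slow recovery from recurrent cytopenia while ending avelumab, but Section 3.1.2 stops PLD whenever avelumab stops, and the Table 7 footnote only partly settles the clash

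*Protocol*

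**What the plan says.** **Linkage rule.** Protocol Section 3.1.2, repeated under Study Treatments in the Protocol Summary: "Patients on Arm B who are discontinued from avelumab treatment for any reason, must also be discontinued from PLD". Both places limit this to PLD given on study and send the patient into the 90-day safety follow-up. Neither makes an exception for haematological toxicity.

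**Table 7, avelumab-PLD column.** For Grade 3 or Grade 4 toxicity that recurs with PLD already at a reduced dose, PLD is held until counts recover, "then resume PLD at the next reduced dose". The same cells deal with avelumab separately. If counts recover in 14 days or fewer, avelumab restarts. If they recover "in > 14 days, permanently discontinue avelumab".

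**Footnote \*\* to Table 7**, attached to the PLD instruction in those cells: "If haematological recovery is achieved within 14 days after the scheduled day of PLD treatment, resume PLD at the previous dose". For late recovery: "If haematological recovery is not achieved 14 days or more after the scheduled day of the course, the patient will permanently discontinue treatment".

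**Text of Section 5.2.8.1**, above the table: "If haematological recovery is not achieved 14 days or more after the scheduled day of the course, the patient will discontinue treatment".

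Table 7 is in force. Section 3.1.2 refers sites to Section 5.2.6 for toxicity management, and Section 5.2.6 lists Table 7. Amendment 2 withdraws only Table 6.

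**The concern.** A site that follows Section 3.1.2 for an Arm B patient with a blood-count toxicity is led to a table whose cells say something else. In one and the same cell, avelumab can end while PLD goes on at a lower dose. The linkage rule excludes exactly that combination.

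What is at stake is whether a patient with repeated severe cytopenia receives more of a cytotoxic drug on study, and at which dose. The last-dose date depends on the answer. So do the 90-day follow-up (Section 6.3.2) and the adverse event reporting period (Section 8.2), both of which count from the last dose.

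**Working it through.** No statistical figure is involved. The check sets the passages side by side and then counts days on an assumed timeline.

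**1. Both 14-day counts start on the scheduled PLD day, and recovery takes more than 14 days.**

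| Source | Avelumab | PLD |
|---|---|---|
| Table 7 cell, read alone | ends | resumes one level lower |
| Table 7 footnote | treatment ends | treatment ends |
| Section 5.2.8.1 text | treatment ends | treatment ends |
| Section 3.1.2 and Summary | (already ended by the cell) | ends |

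There are two outcomes for PLD: the cell resumes it, and the other sources stop it.

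**2. The avelumab count starts earlier.** The footnote counts from the scheduled PLD day. The avelumab bullet gives no starting point. Assume, for illustration, that it runs from onset of the toxicity, with onset on Day 15, PLD due on Day 29 and recovery on Day 35.

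- Avelumab count: 35 − 15 = 20 days, more than 14, so avelumab ends.
- Footnote count: 35 − 29 = 6 days, within 14, so PLD resumes.
- Section 3.1.2: avelumab has ended, so PLD must stop.

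Here the footnote sides with the cell against Section 3.1.2.

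**3. Range of that assumption.** Let onset fall *d* days before the scheduled PLD day and recovery *r* days after it. The footnote and Section 3.1.2 disagree when *d* + *r* > 14 while *r* < 14.

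- *d* = 0: no such *r*; the two agree.
- *d* = 7: *r* from 8 to 13.
- *d* = 14: *r* from 1 to 13.

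The earlier the count starts, the wider the conflict.

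**4. Resumption dose.** For recovery in time, the footnote returns PLD to the dose given before. The marked cells for Grade 3 or 4 recurring at a reduced dose say one level lower. The mismatch also reaches two other marked instructions in the combination column that call for a reduced dose: the first recurrence of Grade 3, and the first Grade 4 event.

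**5. Follow-up dates, same assumed timeline.** Suppose both drugs were last given on Day 1, nothing was given on Day 15, and PLD was either stopped or given on Day 35. The 90-day point is then Day 1 + 90 = Day 91, or Day 35 + 90 = Day 125. The difference is 34 days, and it grows with each further PLD cycle.

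**6. Who is covered.** The avelumab 14-day limit appears only where toxicity recurs with PLD already reduced. On the table's own sequence for Grade 3 (same dose, then reduced dose, then this rule), that is the third occurrence, unless PLD had been reduced for another cause. For Grade 4 it is the second.

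**The case against.** The best answer is that the cell was never meant to be read alone. Its PLD instruction carries the \*\* mark, so the footnote can be taken as its time limit. Section 3.1.2 is also unconditional. On that view the cell wording is merely stale, and a careful reader knows that PLD stops.

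Much of this stands. A reader might infer three rules with three incompatible outcomes. The documents do not support that: when recovery is more than 14 days past the scheduled PLD day, the footnote, Section 5.2.8.1 and Section 3.1.2 all stop PLD, and only the cell text differs. A reader might also infer that every Arm B patient with recurrent Grade 3 or 4 cytopenia is affected. The avelumab limit is confined to recurrence at an already reduced PLD dose. The linkage rule governs on-study PLD only, so nothing follows about treatment outside the trial.

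The footnote still does not settle the matter. It works as a time limit only if the two 14-day counts start together, which is not stated. It also contradicts the marked cells on dose. No order of precedence between Section 3.1.2 and the toxicity tables is given, and Section 5.2.6 allows PLD dose changes, and omissions or delays of either drug, to be handled independently. Tables 9 and 10 show that the clash is avoidable: in the combination arm they end avelumab on recurrence only where PLD has already been stopped for good.

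**Conclusion.** The point holds as an internal contradiction of limited scope. For Arm B patients with Grade 3 or 4 neutropenia or thrombocytopenia recurring at a reduced PLD dose and recovering slowly, current text gives two outcomes for PLD: resume at a lower dose, or stop. The footnote favours stopping when the delay is measured from the scheduled PLD day. It can favour resuming if the avelumab count starts earlier. That second finding rests on an assumed start date, because the protocol gives none; the first does not.

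A reader might go further and infer that the reported OS and PFS results are in doubt. The documents do not support that. Section 9 of the protocol states that the final analysis is complete, and the text reviewed here governs the patients who remain on treatment. The Amendment 2 change log lists the linkage rule, which may explain why Table 7 does not match it, but the finding rests on current wording alone. How many Arm B patients remain is not stated, so the number affected cannot be estimated and may be small. No view is taken on which rule is clinically right.

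**What to change.** Reconcile the Table 7 combination cells, the \*\* footnote, the text of Section 5.2.8.1, Section 3.1.2 and the Protocol Summary so that a single outcome for PLD applies when avelumab is permanently stopped in Arm B. State the day on which the avelumab 14-day count begins. Bring the footnote and the cells it marks to one statement of the resumption dose. The clinical team must decide which rule stands. The cost is protocol wording only; no analysis, sample size or data collection changes.

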3.1.3. Tumor Assessments

Tumor Assessment: Anti-tumor activity will be assessed by radiological tumor assessments per local clinical practice using RECIST version 1.1.

In addition, radiological tumor assessments will also be conducted whenever disease progression is suspected (eg, symptomatic deterioration).

CA-125 is no longer required per protocol but may be performed as clinically necessary.

There is no need to record tumor assessments or CA-125 test results in OC-RCD.

All patients' files and radiologic images will be collected by Parexel.

Please refer to the new SOA in [Appendix 7](#).

3.1.4. Safety Assessments

Safety will be monitored at regular intervals throughout the study by means of laboratory tests and clinical visits as described in the new SOA, ([Appendix 7](#)).

3.1.5. Biomarker Assessments

Effective with Amendment 2, biomarker assessments will no longer be performed/collected.

A key objective of the biomarker analyses that will be performed in this study is to investigate biomarkers that are potentially predictive of treatment benefit with avelumab or the combination of avelumab and PLD. In addition, biomarker studies of tumor and blood biospecimens will be carried out to help further understand the mechanism of action of the PLD plus avelumab combination, as well as potential mechanisms of resistance.

Please refer to the new SOA in [Appendix 7](#).

3.1.6. Pharmacokinetics

Effective with Amendment 2, pharmacokinetic assessments will no longer be performed/collected.

Please refer to the new SOA in [Appendix 7](#).

